4.3 Concomitant Medications/Treatments

The following concomitant medications/treatments are not allowed: immunomodulatory therapies, oral corticosteroids within 1 month of study participation; those taking antihistamines must stop these drugs for one week prior to enrollment and must refrain from taking antihistamines during the duration of the study so as not to interfere with SPT responses; and any other prior investigational interventions.

4.4 Duration of Therapy

Treatment will continue for a minimum of 2 days and a maximum of 7 days per Part 1 of the protocol. Other reasons the medication may be discontinued include:

- Inter-current illness that prevents further administration of treatment;
- Unacceptable adverse event(s);
- Subject decides to withdraw from the study; or
- General or specific changes in the subject's condition render the subject unacceptable for further treatment in the judgment of the investigator.

4.5 Duration of Follow Up

Subjects will be followed until SPT and BAT return to baseline in Part 1, and for up to 6 months after cessation of ibrutinib treatment in Part 2. Subjects removed from treatment for unacceptable adverse events will be followed until resolution or stabilization of the adverse event.

Subjects will be removed from therapy when any of the criteria listed in Section 5.5 apply. The Principal Investigator will be notified. The reason for study removal and the date the subject was removed will be documented in the Case Report Form. The subject will be followed-up per protocol.

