for toxicities (see below). After this visit, subjects will be given ibrutinib (two doses of 420 mg of ibrutinib to start the following day and to be taken orally at 8am exactly 24 hours apart) and return for **Visit 2** to undergo repeat PST and phlebotomy for testing preformed in an identical manner to Visit 1. If two consecutive doses of 420 mg of ibrutinib given 24 hours apart is insufficient to cause >80% inhibition of the SPT and BAT response, subjects will be given two additional doses of 420 mg of ibrutinib to continue to take at 8am exactly 24 hours apart for two more days, and return for **Visit 3** for identical repeat testing as in Visits 1 and 2. If four consecutive doses of 420 mg of ibrutinib given 24 hours apart is insufficient to cause >80% inhibition of the SPT and BAT response, subjects will be given three additional doses of 420 mg of ibrutinib to continue to take 24 hours apart for three more days, and return for **Visit 4** for identical repeat testing as in Visits 1, 2 and 3, where based on preliminary data, we expect SPT and BAT to be suppressed. Once both the SPT and BAT responses are inhibited, no further ibrutinib doses will be given, and subjects will return on a weekly basis until both the peanut/tree nut PST and BAT return to at least 80% of baseline values. At this point, Part 1 will have been completed. At each visit, patients will be monitored for toxicities, including CBC, CMP, and pregnancy testing. Prior to drug initiation and at the end of the trial, an EKG will be performed.

Clinical protocol for part 1 (top) and part 2 (bottom). * or - = predicted response; ??? = question to be answered; * = if needed

and subjects will return on a weekly basis until both the peanut/tree nut PST and BAT return to at least 80% of baseline values. At this point, Part 1 will have been completed. At each visit, patients will be monitored for toxicities, including CBC, CMP, and pregnancy testing. Prior to drug initiation and at the end of the trial, an EKG will be performed.

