Part 2: Visit 1 will be identical to those for Part 1 except that subjects will take a higher dose of ibrutinib (560mg daily) for 2 days and a single-blind, placebo-controlled (SBPC) graded food challenge of up to 8 mg of peanut or tree nut protein, administered over escalating doses, will be performed in a monitored at the study site in a clinical research unit (CRU) setting. Prior to the SBPC food challenge, 30 mL of peripheral blood will be collected for BAT, sIgE to peanut and components, as well as for total IgE, eosinophil and basophil enumeration. During the challenge, subjects will be repeatedly assessed for signs and symptoms of food-induced anaphylaxis between each dose per food challenge protocol. This visit will establish each subject's baseline threshold dose for peanut/tree nut reactivity.

Once a confirmed reaction occurs, the food challenge will be terminated and the reaction treated until it has resolved. Within 15 minutes of a positive challenge, an additional 10 mL of blood will be drawn for mast cell microparticle analysis. After a minimum of a two week recovery period, each subject will then begin taking ibrutinib 560 mg orally daily for 2 days, which is the minimum number of doses that

demonstrate efficacy as determined in Part 1. Two hours after the final dose, subjects will return to the study site for **Visit 2**, and PST and SBPC food challenges will be repeated to establish each subject's new threshold dose for peanut/tree nut reactivity while on ibrutinib, and with repeat post-challenge blood collection for mast cell microparticle analysis. At this point of the protocol, ibrutinib dosing will be stopped. Follow up visits starting 3 months after cessation of ibrutinib will be conducted to repeat toxicity labs and skin testing.

STUDY SUMMARY

Title	Inhibition of Anaphylaxis by Ibrutinib
Protocol Number	BB20150924
Phase	Phase 2
Methodology	Open label study to determine dosing and safety of Ibrutinib for the treatment of food allergy
Study Duration	12 weeks
Study Center(s)	Single-center

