5.1.13 Spirometry

To be performed before SBFC if the patient has a history of asthma or exercise-induced bronchospasm.

5.2 Procedures During Treatment (Part 1)**5.2.1 Screening visit (Day 0) (Screening visit testing will be completed before drug administration)****Screening:**

- Physical exam, vital signs
- CBC
- CMP
- Immunoglobulin levels
- EKG
- Urine Pregnancy test (if required)

Procedures (to be done only if labs and EKG are within normal limits):

- Skin-prick testing
- Basophil activation test

5.2.2 Day 2 (or 4 or 7 depending on when skin testing and basophil activation test return to baseline)

- Skin prick testing
- Basophil activation test
- Hematology
- Serum chemistries
- Immunoglobulin levels

5.2.3 After treatment termination (Termination and End of Study visits; time point determined when both skin prick testing and basophil activation testing return to baseline)

- Physical exam, vital signs
- Hematology
- Serum chemistries
- Immunoglobulin levels
- EKG
- Urine Pregnancy test (if required)

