5.4 Follow-up Procedures

Subjects will be followed every month after completion of (or early withdrawal from) study treatment until testing returns to baseline. Toxicity monitoring will be repeated (including hematology, serum chemistries, QUIGs, sIgE) at 3 months after cessation of ibrutinib; if at this time they are not yet back to baseline, they will be repeated at 6 months.

- Physical exam, vital signs
- Urine Pregnancy test (if required)
- CBC
- CMP

- Immunoglobulin levels
- Skin prick testing

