5.5 Time and Events Table

5.4.1. Part 1

Visit	1	2	3 ^a	4/Early Termination	End-of-Study
	Screening / Day 0	Day 2	Day 4 or Day 7	Every 7 days until all allergy testing returns to baseline positive	Final Visit when all allergy testing is positive
Informed Consent	X				
Skin prick testing	X	X	X	X	
Basophil activation test	X	X	X	X	
History and PE	X				X
Toxicity (include DLT) Evaluations	X	X	X	X	X
CBC	X	X	X	X	X
CMP	X	X	X	X	X
EKG	X				X
Urine pregnancy testing ^b	X	X	X	X	X

^a If required

^b Females of child-bearing potential only

5.4.2. Part 2

Visit	1	2	3
	Screeing / Day 0	Day 2	Follow up (3 and/or 6 months after Visit 2)
Informed Consent	X		
Skin prick testing	X	X	X
Basophil activation test	X	X	
SBPC food challenge	X	X	
History and PE	X	X	X

Toxicity (include DLT) Evaluations	X	X	X
CBC	X	X	X
CMP	X	X	X
EKG	X	X	
Urine pregnancy test ^b	X		

^b Females of child-bearing potential only

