8.2 Steps to Determine If an Adverse Event Requires Expedited Reporting

Step 1: Identify the type of adverse event.

Step 2: Grade the adverse event.

Step 3: Determine whether the adverse event is related to the protocol therapy
Attribution categories are as follows:

- Definite – The AE *is clearly related* to the study treatment.
- Probable – The AE *is likely related* to the study treatment.
- Possible – The AE *may be related* to the study treatment.
- Unrelated – The AE *is clearly NOT related* to the study treatment.

Note: This includes all events that occur within 30 days of the last dose of protocol treatment. Any event that occurs more than 30 days after the last dose of treatment and is attributed (possibly, probably, or definitely) to the agent(s) must also be reported accordingly.

Step 4: Determine the prior experience of the adverse event.

Expected events are those that have been previously identified as resulting from administration of the agent. An adverse event is considered unexpected, for expedited reporting purposes only, when either the type of event or the severity of the event is not listed in:

- the current known adverse events listed in the Agent Information Section of this protocol;
- the drug package insert;
- the current Investigator's Brochure

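### Part 1 follow-up ends on skin-test and basophil recovery with no minimum time after the last dose, and the scope of section 5.4 is unclear, so planned contact may not span the 30-day adverse-event window

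*Combined protocol and SAP*

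**What the plan says.** **Part 1.** Section 4.5: "Subjects will be followed until SPT and BAT return to baseline in Part 1". The study schema: "subjects will return on a weekly basis until both the peanut/tree nut PST and BAT return to at least 80% of baseline values" (PST appears to mean the skin test), at which point Part 1 is complete. Section 5.2.3 places the termination and end-of-study visits at a "time point determined when both skin prick testing and basophil activation testing return to baseline". The Part 1 table in 5.5 has a visit every 7 days and then a "Final Visit when all allergy testing is positive". The recovery criterion is worded differently in these places (80% of baseline, baseline, positive), but in each the exit depends on allergy-test recovery and not on days since the last dose.

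**Part 2.** The schema: "Follow up visits starting 3 months after cessation of ibrutinib will be conducted to repeat toxicity labs and skin testing". The Part 2 table heads its last column "Follow up (3 and/or 6 months after Visit 2". Section 5.4, which names no part, says "Subjects will be followed every month after completion of (or early withdrawal from) study treatment until testing returns to baseline" and adds toxicity monitoring at 3 months, repeated at 6 months if values are not back to baseline.

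**Event window.** A note in 8.2 reads "This includes all events that occur within 30 days of the last dose of protocol treatment". It also takes in later events attributed to the drug. Section 8.3.1 applies the same 30 days to serious events, whatever their attribution.

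**The concern.** Objective 2.2.1 is to describe the adverse events of a short ibrutinib course, and 2.3 names bleeding, hepatotoxicity and renal toxicity for monitoring. Skin-test and basophil recovery measure allergic reactivity, not those toxicities. Tying the end of Part 1 follow-up to them makes the length of planned safety observation depend on how fast the anti-allergic effect wears off. It can therefore differ between subjects and can stop before day 30.

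A symptomatic event that starts after the last planned visit but before day 30 falls in the reporting window, yet no contact inside that window is planned to ask about it. The follow-until-resolution rules in 4.5 and 8.0 apply to events already known, and the pill diary in Appendix 1 records only pills and times. In Part 2 the sections disagree on whether anyone sees the subject between Visit 2 and month 3. With six subjects per part, one unrecorded event would matter to a descriptive safety summary.

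**Working it through.** The plan states no figure for this, so there is nothing to reproduce. The check sets visit days against the 30-day window.

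**Inputs**
- Event window: 30 days after the last dose (8.2, 8.3.1).
- Part 1 post-treatment visits: every 7 days until recovery (schema; Part 1 table).
- Part 2 Visit 2: two hours after the final dose, so day 0 (schema).
- Part 2 next contact: 3 months (schema, table) or one month (5.4).
- Subjects: 6 in each part (4.1).
- Recovery time: not given. It is itself under study (objective 2.2.3), so a range is shown.

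**Assumptions**
- The visit that shows recovery is the last one. If the End-of-Study visit is later, the gap is smaller.
- The statement in 4.1 that Part 1 ends once both tests are negative refers to dosing only.
- Calendar A counts weekly visits from the last dose. Calendar B counts them from a test visit one day after the last dose.

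**Part 1.** Days of the window after the last planned contact = max(0, 30 − exit day).

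| Recovery shown at weekly visit | A: exit day | A: days left (share of 30) | B: exit day | B: days left (share of 30) |
|---|---|---|---|---|
| 1 | 7 | 23 (76.7%) | 8 | 22 (73.3%) |
| 2 | 14 | 16 (53.3%) | 15 | 15 (50.0%) |
| 3 | 21 | 9 (30.0%) | 22 | 8 (26.7%) |
| 4 | 28 | 2 (6.7%) | 29 | 1 (3.3%) |
| 5 | 35 | 0 | 36 | 0 |

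**If 5.4 covers Part 1.** Its monthly visits stop once testing is back to baseline, so a subject who recovers at visit 1 has no required contact until the 3-month toxicity check at about day 91. That is 91 − 7 = 84 days after the last visit. The check can still elicit an event from days 8 to 30, but 91 − 30 = 61 to 91 − 8 = 83 days after onset.

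**If 5.4 covers Part 2 only.** The first monthly visit falls at about day 28 to 31, leaving max(0, 30 − 28) = 2 down to 0 days, provided testing was not already at baseline at Visit 2. Under the schema and Part 2 table, no contact is planned from day 0 to about day 91, which is 91 − 30 = 61 days after the window closes. A site cannot tell which schedule applies.

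**Which reading of 5.4 is likelier?** Sections 5.2 and 5.3 are labelled by part and 5.4 is not. Its 3- and 6-month timing, its list (skin testing without the basophil test) and the wording of 4.5 point to Part 2. Its literal wording covers everyone.

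**The case against.** Several objections have force.

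- **Section 5.4 may cover Part 1.** It refers to subjects without restriction, and the 12-week study duration in the summary would fit a 3-month contact, though it does not prove one. A reader might infer from 4.5 and the Part 1 table that nobody contacts a Part 1 subject after test recovery. The documents do not support that as a flat statement. What stands is that, on either reading, an early recoverer has no required contact between recovery and at least month 3.
- **The 30-day text sets reporting scope.** In 8.2 it is a note on expedited reporting, and in 8.3.1 the clock runs from learning of an event. A reader might infer that the plan breaks its own rule. It does not: neither section promises active follow-up to day 30. The schedule simply gives the window no reliable source of information.
- **The exit is not arbitrary.** Exposure is 2 to 7 doses, the half-life is 4 to 6 hours (1.2), and toxicity evaluation, blood count and chemistry are done at each weekly visit and at End-of-Study. This lowers the likelihood of late events, although binding is irreversible and the plan itself chose 30 days.
- **The gaps are upper bounds.** The End-of-Study column in the Part 1 table has no skin or basophil test ticked, and 5.2.3 speaks of visits in the plural. Both suggest a separate, possibly later visit. This objection is accepted.
- **Subjects may have been told to report events.** The consent pages are not available, so such instructions cannot be ruled out. They would still be passive capture.

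**Conclusion.** The concern holds as a minor point. Part 1 has no minimum safety follow-up after the last dose. For a subject who recovers at weekly visits 1 to 4, up to about 23, 16, 9 or 2 days of the 30-day window may pass without planned contact (22, 15, 8 or 1 on the other calendar). With recovery at visit 5 or later the gap is zero. The range rests on the stated calendar assumptions and on unknown recovery times, so 23 days is the extreme case, not an expected value.

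The scope of 5.4 needs settling whichever way it is read. It either leaves Part 1 early recoverers without required contact until month 3 or conflicts with the Part 2 schema and table.

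A reader might go further and infer that events are lost or results biased. The documents do not support this. Part 2 events can still be elicited at 3 months and still count, and 10.3 plans descriptive within-subject summaries only, so no planned comparison is affected. The effect is on how completely, and over how uniform a period, adverse events are described for objective 2.2.1.

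**What to change.** 1. In 4.5 and both tables in 5.5, add one adverse-event phone contact at about day 30 after the last dose in both parts. A scheduled visit on about days 30 to 37 can replace it. This covers the window whatever the recovery date.
2. State which part or parts 5.4 covers, and align it with the Part 2 table: either add the monthly visits to the table or remove them from 5.4.
3. State in 3.2.1 and 4.3 that the antihistamine restriction ends at the last skin-test visit. Both sections now bar antihistamines for the whole study in order to protect the skin test, so a longer safety follow-up would otherwise prolong the restriction for food-allergic adults with no benefit.

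**Cost.** Wording changes in these sections and two tables, and at most 6 + 6 = 12 calls. A Part 1 subject who recovers at the first weekly visit stays in safety follow-up for up to 30 − 7 = 23 days longer (30 − 8 = 22 on the other calendar). With item 3 in place, those days carry no antihistamine restriction. Total follow-up in Part 2 is not lengthened.

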4.6 Subject Replacement

Subjects who withdraw voluntarily from the study, but were tolerating the drug will be replaced. Subjects who drop out or miss doses due to toxicity will not be replaced since these subjects will be considered to have experienced a dose limiting toxicity.

5.0 STUDY PROCEDURES**5.1 Screening/Baseline Procedures**

Assessments performed exclusively to determine eligibility for this study will be done only after obtaining written informed consent. Assessments performed for clinical indications (not exclusively to determine study eligibility) may be used for baseline values even if the studies were done before informed consent was obtained.

All screening procedures must be performed within 14 days prior to start of treatment. The screening procedures include:

5.1.1 Informed Consent

Informed consent will be obtained per IRB and GCP guidelines.

5.1.2 Medical history

Complete medical and surgical history, history of infections will be obtained.

5.1.3 Demographics

Age, gender, race, ethnicity will be obtained.

5.1.4 Review subject eligibility criteria

Subjects will be screened to ensure they meet inclusion and exclusion criteria, including history and prior laboratory testing consistent with a diagnosis of IgE mediated food allergy.

5.1.5 Review previous and concomitant medications

Medications will be reviewed and documented.

5.1.6 Physical exam including vital signs, height and weight

Vital signs (temperature, pulse, respirations, blood pressure), height, weight and basic full physical exam will be performed by study physicians.

5.1.7 Adverse event assessment

Baseline adverse events will be assessed. This will include a CMP and CBC, EKG. See section 6 for Adverse Event monitoring and reporting.

5.1.8 Hematology

Baseline CBC will be performed.

5.1.9 Blood draw for correlative studies

See Section 9.0 for details.

5.1.10 Serum chemistries

Comprehensive metabolic panel (CMP) to include: albumin, alkaline phosphatase, ALT/SGPT, AST/SGOT, BUN, creatinine, electrolytes (sodium, potassium, calcium, chloride, bicarbonate), glucose, and total bilirubin.

5.1.11 Pregnancy test (for females of child bearing potential)

See section 3.1.6.1 for definition.

5.1.12 Immunoglobulin levels

Total quantitative immunoglobulins (QUIGs), including IgG, IgA, IgM, and IgE, as well as serum specific IgE for peanut/tree nuts will be monitored

5.1.13 Spirometry

To be performed before SBFC if the patient has a history of asthma or exercise-induced bronchospasm.

5.2 Procedures During Treatment (Part 1)**5.2.1 Screening visit (Day 0) (Screening visit testing will be completed before drug administration)****Screening:**

- Physical exam, vital signs
- CBC
- CMP
- Immunoglobulin levels
- EKG
- Urine Pregnancy test (if required)

Procedures (to be done only if labs and EKG are within normal limits):

- Skin-prick testing
- Basophil activation test

5.2.2 Day 2 (or 4 or 7 depending on when skin testing and basophil activation test return to baseline)

- Skin prick testing
- Basophil activation test
- Hematology
- Serum chemistries
- Immunoglobulin levels

5.2.3 After treatment termination (Termination and End of Study visits; time point determined when both skin prick testing and basophil activation testing return to baseline)

- Physical exam, vital signs
- Hematology
- Serum chemistries
- Immunoglobulin levels
- EKG
- Urine Pregnancy test (if required)

5.3 Procedures During Treatment (Part 2)

5.3.1 Screening/Baseline visit (Visit 1)

Screening:

- Physical exam, vital signs
- Urine Pregnancy test (if required)
- CBC
- CMP
- Immunoglobulin levels
- EKG
- Spirometry (only if the subject has a history of asthma)

Procedures (to be done only if labs and EKG are within normal limits)

- Skin prick testing
- Basophil activation test
- SBPC oral food challenge as follows:

All oral food challenges (OFC) shall be performed as single (patient)-blinded, placebo controlled food challenges according to standard published guidelines (11, 12). Placebo challenge and active challenge will be performed in that order on the same day if the subject has no symptoms during the first (placebo) challenge. If a reaction requiring treatment occurs during the first challenge, the next challenge should not be performed until the symptoms have subsided. Oral food challenge to peanut or tree nut protein will be performed according to standard operating procedure. At physician discretion, based upon history and possible subjective or very mild objective symptoms during a challenge, dosing intervals may be extended.

Actions to minimize risk of severe allergic reactions during oral food challenge (OFC):
Prior to the OFC visit, subjects will be told to contact study staff about asthma and seasonal allergy symptoms, fever, acute infections including upper respiratory infections, rashes or change in status of chronic medical conditions. OFCs will be rescheduled in the event that any of these occur. Study staff will contact subjects 1-3 days before the OFC to inquire about recent symptoms.

All OFCs will be conducted in the Clinical Research Unit within the main hospital. Intravenous access will be obtained before the OFC begins. Emergency medications (epinephrine, diphenhydramine, cetirizine, albuterol, ranitidine) will be immediately accessible in the subject's room. All OFCs will be conducted by trained personnel and supervised by a clinician with experience in performing OFCs and trained in the treatment of anaphylaxis. Spirometry (assessment of pulmonary function) will be performed prior to the onset of the OFC. Vital signs and pulse oximetry will be obtained at baseline and prior to each dose of the food allergen and q15 minutes thereafter with an observation period of at least 2 hours after the last dose is consumed (longer should a reaction occur). The OFC will begin with a low dose, which will increase incrementally. At physician discretion, based upon history and possible subjective or very mild objective symptoms during a challenge, dosing intervals may be extended. The procedure will be stopped when clear objective symptoms are noted.

Subjects will be discharged after a period of observation appropriate to the nature of the symptoms. They will receive information regarding possible delayed manifestations and home treatment. All subjects will be provided with an epinephrine auto-injector to take home (if they do not have one already) and instructions on how and when to use it.

5.3.2 Visit 2

- Skin prick testing
- Basophil activation test
- CBC
- CMP
- Immunoglobulin levels
- Spirometry (only if the patient has a history of asthma)
- SBPC oral food challenge as follows:

All oral food challenges (OFC) shall be performed as single(patient)-blind, placebo controlled food challenges according to standard published guidelines (11, 12). Placebo challenge and active challenge will be performed in that order on the same day if the subject has no symptoms during the first (placebo) challenge. If a reaction requiring treatment occurs during the first challenge, the next challenge should not be performed until the symptoms have subsided. Oral food challenge to peanut or tree nut protein will be performed according to standard operating procedure. At physician discretion, based upon history and possible subjective or very mild objective symptoms during a challenge, dosing intervals may be extended.

Actions to minimize risk of severe allergic reactions during oral food challenge (OFC):
Prior to the OFC visit, subjects will be told to contact study staff about asthma and seasonal allergy symptoms, fever, acute infections including upper respiratory infections, rashes or change in status of chronic medical conditions. OFCs will be rescheduled in the event that any of these occur. Study staff will contact subjects 1-3 days before the OFC to inquire about recent symptoms.

All OFCs will be conducted in the Clinical Research Unit within the main hospital. Intravenous access will be obtained before the OFC begins. Emergency medications (epinephrine, diphenhydramine, cetirizine, albuterol, ranitidine) will be immediately accessible in the subject's room. All OFCs will be conducted by trained personnel and supervised by a clinician with experience in performing OFCs and trained in the treatment of anaphylaxis. Spirometry (assessment of pulmonary function) will be performed prior to the onset of the OFC. Vital signs and pulse oximetry will be obtained at baseline and prior to each dose of the food allergen and q15 minutes thereafter with an observation period of at least 2 hours after the last dose is consumed (longer should a reaction occur). The OFC will begin with a low dose, which will increase incrementally. At physician discretion, based upon history and possible subjective or very mild objective symptoms during a challenge, dosing intervals may be extended. The procedure will be stopped when clear objective symptoms are noted.

Subjects will be discharged after a period of observation appropriate to the nature of the symptoms. They will receive information regarding possible delayed manifestations and home treatment. All subjects will be provided with an epinephrine auto-injector to take home (if they do not have one already) and instructions on how and when to use it.

